3.5 Evaluation of Circulating Tumor Cells (CTC)

Circulating tumor cells (CTC) can be detected in the blood from patients with various primary or metastatic carcinomas.²⁵⁻²⁹ Recently the development of immunomagnetic separation strategies has increased the sensitivity of these assays.^{28,29} Several studies have reported that the presence of CTC predicted shortened disease free and overall survival times. These studies demonstrate that detection of CTC correlates with prognosis at baseline and that changes in CTC levels during and after treatment may be more predictive than other measures.³⁰⁻³⁴ Monoclonal antibody based therapy (trastuzumab) with or without additional chemotherapy was particularly effective at eliminating CTC. This was associated with improved disease free and overall survival.²⁸

Use of peripheral blood immunomagnetically enriched for tumor cells using labeled antibodies targeting epithelial cell surface markers on breast cancer cells and quantitated using a CellSpotterAnalyzer is now FDA approved for this purpose in breast cancer patients. Veridex, LLC. has provided MSKCC with a CellSpotterAnalyzer for this purpose in patients with prostate and breast cancer. To date, [name], Chief of the MSKCC Department of Clinical Laboratories, has validated the assay in prostate cancer patient using the same labeled antibodies which are FDA approved for use in breast cancer patients.

Two studies have identified CTC in approximately 95% of breast cancer patients with Stage I/II disease prior to surgery.^{35,26} After resection of all known disease, 30% of patients continued to have CTC that persisted for at least 2 weeks. The patients that we propose to evaluate are patients at a high risk for recurrence. We estimate that at least 30% of these patients will have demonstrable CTC.

In this study, CTC will be evaluated in an exploratory manner to determine whether they can be detected in this patient population at baseline and if so whether there is evidence

of a decline in those patients who have an immune response. CTC will be monitored prior to, during and after injection with sLe^a-KLH plus QS-21. The patient and their primary oncologist will be notified of all CTC results. These results will be used for research purposes and will not be used during the study to alter clinical care. Although some physicians at other centers may use CTC results to evaluate response to therapy, this is not considered standard care at MSKCC.

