4.1 OVERVIEW OF STUDY DESIGN/INTERVENTION

4.2 Design

This is a pilot study designed to assess the safety and immunogenicity of a sLe^a-KLH plus QS-21 construct in patients with metastatic breast cancer. Initially 3 patients will be accrued to the study at a 10 mcg dose of sLe^a. If safe, then 10 patients will be accrued at the 30 mcg dose of sLe^a. If 6 or more of these 10 patients have an immune response at any time point then an additional 10 patients will be accrued and injected with a higher dose of QS-21. Toxicities will be monitored during the study. Patients will be instructed to complete a patient diary and document any side effects.

Patient blood samples will be evaluated for an IgG and IgM antibody response to sLe^a and breast cancer cells expressing this antigen. Immunological response for a patient is defined as an antibody response of greater than 1:80 if baseline value was 0 and at least an increase of 8-fold if baseline value is greater than 0. Patient blood samples will also be monitored for the presence of circulating tumor cells pre study and then during weeks 5, 13, and 23.

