4.3 Intervention

Patients will receive sLe^a-KLH plus QS-21 subcutaneously during weeks 1,2,3,7 and 19. The first 3 patients will receive a 10 mcg dose of sLe^a and subsequently all patients will receive a 30 mcg dose of sLe^a. The dose of QS-21 is 100 mcg for the initial 13 patients. If immune responses are observed at the 100 mcg level of QS-21 then the dose of QS-21 will be escalated to 150 mcg, in a subsequent group of patients during weeks 1, 7 and 19. Blood samples will be obtained pre study and during weeks 1,2,3,5,7,9,13, 19 and 23 to assess for immune response.

sLe^a is one of multiple antigens found on breast cancer cells. Data from this trial will be used to determine whether the sLe^a antigen will be included in a future polyvalent construct. Ultimately we plan a multicenter randomized clinical trial to assess potential clinical benefit of immunization with a polyvalent construct in high risk breast cancer patients.

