8.1 PRETREATMENT EVALUATION

Within 2 weeks of the first injection:

Pregnancy test for premenopausal patients

Within 3 weeks of the first injection:

- Complete history and physical examination
- Complete blood cell count with differential and platelet count (CBC)
- Comprehensive panel (COMP): aspartate aminotransferase (AST), alanine aminotransferase (ALT), albumin, alkaline phosphatase, bilirubin, calcium, creatinine, glucose, total protein, BUN, sodium, potassium, chloride, C02
- CEA, CA153(or BR27-29 or CA27-29)

- Thyroid stimulating hormone (TSH) level
- Urinalysis
- Rectal examination with Hemoccult
- Blood (3 red-top tubes) for immune response studies will be sent to [name] laboratory in [name]. An additional 7.5 ml of blood will be drawn in special tubes to go to [name] lab in Clinical Chemistry for assessment of circulating tumor cells. These blood samples may be drawn on the day of the first injection, but prior to the injection.

Within 4 weeks of the first injection:

Imaging and Diagnostic Studies

- CT scan of the chest/abdomen/pelvis
- Radionuclide bone scan

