10.3 Circulating Tumor Cell Methodology

Epithelial cell adhesion molecule (EpCAM) is used to concentrate circulating epithelial tumor cells from a 7.5 ml peripheral blood specimen. A semi-automated system called CellSearch, uses EpCAM antibody-based immunomagnetic capture of epithelial cells to identify and isolate circulating tumor cells (CTC).

Immunomagnetically captured CTCs are stained and enumerated using specially prepared buffers and three immunofluorescent markers: DAPI to detect cells with intact nuclei; Cytokeratin-PE to detect epithelial cells; and CD-45-APC to detect leukocytes. CTCs are defined as DAPI(+), CK-PE(+) and CD-45(-) cells. Digitally archived images of candidate CTCs meeting these criteria also must meet standardized morphologic inspection.

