14.0 BIOSTATISTICS

This is a pilot study designed to assess the safety and immunogenicity of immunization with sLe^a-KLH plus QS-21 in patients with high risk breast cancer. If immune responses are observed at the 100 mcg level of QS-21 then QS-21 will be escalated to the 150mcg level.

The immunization schedule comprises five injections administered during weeks 1,2,3,7 and 19. The primary endpoint of this trial is to evaluate immunological response to this single antigen and evaluate toxicity. Immunological response for a patient is defined as an antibody response of greater than 1:80 if baseline value was 0 and at least an increase of 8-fold if baseline value is greater than 0. Initially, three patients will be accrued to the study at a dose of 10 mcg of sLe^a. If safe, then ten patients will be accrued to the study at the full 30mcg sLe^a dose. If 6 or more of these 10 patients have an immune response at any time point then an additional 10 patients may be accrued and receive sLe^a-KLH plus QS-21 (at 150mcg) during weeks 1, 7 and 19. This sample size is chosen to minimize the total number of patients who need to be immunized to identify a promising agent with a probability of an immunological response greater than 50% in a series of immunization trials. The error rates of missing a promising agent or selecting a nonpromising agent are set to be at most 10%.³⁶

At the end of the trial a qualitative assessment of the number of responses and frequency of toxicities will be made to determine which dose of QS-21 will be carried forward in future studies.

Severe toxicities are not anticipated. Toxicities will be tabulated according to the NCI CTC version 3.0. Any grade 3 or greater toxicity (excluding grade 3 lymphopenia) or grade 2 or greater allergic/immunologic toxicity (except isolated fever and/or flushing) will result in removal of the patient from the study. Since the above listed toxicities are unexpected, any event of this sort will result in suspension of the study pending further investigation. Descriptive statistics summarizing the antibody responses will be provided for each patient. The length of the study will be approximately 1-2 years.

Circulating tumor cells (CTC) will be evaluated in an exploratory manner to determine whether CTC can be detected in this patient population at baseline and if so whether there is evidence of a decline in those patients who have an immune response.

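### The exploratory CTC analysis looks for a decline in immune responders only, against one baseline tube and with no comparison group or timing rule, so chance falls from low counts can pass as declines

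*Combined protocol and SAP*

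**What the plan says.** - **Question and status.** Monitoring CTC before, during and after injection is the only secondary objective (Section 2.1). Section 14.0 says "Circulating tumor cells (CTC) will be evaluated in an exploratory manner" and asks "whether CTC can be detected in this patient population at baseline and if so whether there is evidence of a decline in those patients who" show an immune response. Section 3.5 puts the same question. Neither section defines a decline, names a comparison group, or says how patients with 0 at baseline are handled.
- **Expected detection.** Section 3.5: "We estimate that at least 30% of these patients will have demonstrable CTC".
- **Measurement.** Section 10.3: "Epithelial cell adhesion molecule (EpCAM) is used to concentrate circulating epithelial tumor cells from a 7.5 ml peripheral blood specimen". Section 8.1 provides one pre-treatment sample: "An additional 7.5 ml of blood will be drawn in special tubes".
- **CTC draws.** Section 4.2 has patients "monitored for the presence of circulating tumor cells pre study and then during weeks 5, 13, and 23". The evaluation table in Section 10.0, as it reads in the extracted text, marks pre-study, weeks 5, 9 and 19, and every 3 months. Week 5 is in both.
- **Serology.** Section 4.3: "Blood samples will be obtained pre study and during weeks 1,2,3,5,7,9,13, 19 and 23 to assess for immune response".
- **Response.** Sections 4.2 and 14.0 define it by titre (above 1:80 from a baseline of 0, otherwise at least an 8-fold rise), with no time limit.
- **Use.** Sections 3.5 and 10.1 say CTC results will not alter clinical care during the study.

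**The concern.** Two features of the question can make a decline appear with no vaccine effect.

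First, a count can fall only if it starts at 1 or more. Counting falls therefore looks at patients whose single baseline tube happened to be positive, and low positive counts tend to be followed by lower ones. Non-responders would show the same chance falls and so expose the artefact, but the question is put for responders only.

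Second, response status may be settled long after a CTC draw. A week-5 fall in a patient who first meets the titre definition at a later visit would still be a fall in an immune responder.

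What is at stake is interpretation. Section 3.5 presents CTC change as prognostic and reports that antibody-based clearance of CTC went with better survival. Falls among responders would invite that reading.

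**Working it through.** The plan gives no threshold, test, power or sample size for CTC, so there is no CTC figure to reproduce. The check asks how often a fall appears when nothing changes.

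**Inputs from the protocol:** 30% detectable at baseline (Section 3.5 gives this as a minimum); one baseline tube; three later draws (Section 4.2); 13 to 23 patients (3 + 10, plus a conditional 10).

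**Assumptions:** each count is Poisson and each patient's true mean is constant over all four tubes. The documents give no count distribution, so the between-patient spread is varied while detection is held at 30%:
- Common mean: exp(-m) = 0.70, so m = 0.357 cells per tube.
- Gamma-distributed means with shape k: (1 + m/k)^(-k) = 0.70, so m = k(0.70^(-1/k) - 1). Smaller k means more spread.

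**Results with no true change, patients with baseline count of at least 1 (simulation):**

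| Spread | Mean | One later draw lower | One later draw higher | Lower on at least 1 of 3 |
|---|---|---|---|---|
| Common mean | 0.357 | 74% | 4% | 98% |
| k = 1 | 0.43 | 66% | 12% | 91% |
| k = 0.5 | 0.52 | 61% | 17% | 86% |
| k = 0.25 | 0.79 | 55% | 25% | 81% |
| k = 0.1 | 3.44 | 51% | 35% | 76% |

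**Why this happens (common mean).** Over all patients, falls and rises each occur in 22.3% and the mean change is 0. Every fall starts from a positive baseline, so among positives falls are 0.223/0.30 = 74%. Most rises start from zero: 0.70 × 0.30 = 0.21. That leaves 0.223 - 0.21 = 0.013 from positive baselines, or 0.013/0.30 = 4%.

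**Higher counts.** At a common mean of 5, one later draw is lower in 44% and higher in 43%; at 20, 47% each way. The selection effect has gone. Even so, 69% and 72% read lower on at least one of three draws, because there are several looks and any lower count qualifies. Falls of at least half occur on one draw in 19% at mean 5 and 2% at mean 20. These means imply detection of 99% or more, so they are sensitivity cases, not the protocol's 30%.

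**Patients affected.** With 23 patients, 23 × 0.30 = 6.9 are baseline-positive. At an assumed 60-80% response rate unrelated to CTC status, 4.1 to 5.5 of these are responders and 1.4 to 2.8 are non-responders. If any lower count counts, 4.1 × 0.76 = 3.1 to 5.5 × 0.98 = 5.4 responders show a fall at some visit by chance.

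**Timing.** After the week-5 CTC draw come two of the five injections (weeks 7 and 19) and five serology draws (weeks 7, 9, 13, 19 and 23). A patient first meeting the definition at any of those five is a responder, and the week-5 count precedes that.

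**The case against.** The strongest reply is that the text does not contain the biased analysis. Several stronger readings are tempting, and the documents do not support them.

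- **That baseline-zero patients are excluded.** No section says so. The conditional in the CTC sentence can refer to the population, and Section 12.2 aims to account for all patients. A mean change over all responders, zeros included, would not carry the selection effect. This stands; the gap is that the plan does not say which summary it means.
- **That the summary can show only falls.** Baseline-positive patients can also rise, in 4-35% of cases on one draw in the table.
- **That the CTC analysis uses responders at any time point.** Those words belong to the escalation rule in Section 4.2: "If 6 or more of these 10 patients have an immune response at any time point then an additional 10 patients will be accrued". The CTC sentence sets no window. The timing point rests on the untimed response definition instead.
- **That a week-5 fall precedes the antibody.** Week 5 follows three injections, and a titre below the threshold is still antibody. Only a fall before the response definition is met can be shown.
- **That a null vaccine would show declines in most evaluable responders.** This depends on the count distribution and on counting any lower reading. At a common mean of 5, a single draw is lower in 44%.

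The consequence is also limited. The analysis is exploratory and has no error rate. The QS-21 choice rests on responses and toxicities (Section 14.0), and use of the antigen in a polyvalent vaccine rests on tolerability and immunogenicity (Section 3.4). With so few CTC-positive responders, the result is a case listing. All of this stands and limits the point to reporting. It does not supply the missing comparison or timing rule.

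**Conclusion.** The concern holds in a limited form. A responder-only search for CTC declines, from one baseline tube and with no comparison group, cannot separate a vaccine effect from re-sampling when counts are low. With 30% detection, Poisson counting and no true change, 51-74% of baseline-positive patients read lower on one later draw and 76-98% on at least one of three. The range reflects the assumed between-patient spread, and the multi-draw figures assume that any lower count is called a decline. Where counts are higher, single-draw falls and rises balance. Separately, the untimed response definition lets a week-5 fall be credited to a response first met later. The effect is on how an exploratory result is read; it does not touch the primary endpoints, the escalation rule or patient care. The change is worth making because it costs almost nothing.

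**What to change.** In Sections 3.5 and 14.0:

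1. Report each patient's CTC counts and change from baseline for all patients, including those with 0 at baseline and any rises, with responders beside non-responders.
2. Show whether each CTC draw came before or after that patient's first responding serology, and describe only later draws as following an immune response.
3. State that small falls from low counts are expected by chance.
4. Reconcile the CTC draw weeks in Section 4.2 with the table in Section 10.0. Check the source table first, since extraction may have shifted its columns.

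I would not require a decline to exceed Poisson error on two consecutive draws. In an exact comparison of two tubes at the 5% level, even a fall to zero needs a baseline of at least 5 cells one-sided (0.5^5 = 0.031) or 6 two-sided (2 × 0.5^6 = 0.031). Under the common-mean model only about 0.01% of baseline-positive patients reach 5 cells (leading term 0.70 × 0.357^5/120/0.30 = 0.0001), so the question could hardly be answered. More patients would reach it with wide spread, but that cannot be relied on.

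No new samples are needed. The cost is slightly more tabulation and a weaker exploratory claim of decline.

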16.1 DATA MANAGEMENT ISSUES

A data profile in Appendix A will be completed for all patients.

A Research Study Assistant (RSA) will be assigned to the study. The responsibilities of the RSA include project compliance, data collection, abstraction and entry, data reporting, regulatory monitoring, problem resolution and prioritization and coordination of activities of the protocol study team.

The data collected for this study will be entered into a secure database at MKSCC. Data from this trial will be entered in the Clinical Research Data Base (CRDB). Source documentation will be available to support the computerized patient record.

16.2 Quality Assurance

Weekly registration reports will be generated to monitor patient accruals and completeness of registration data. Routine data quality reports will be generated to assess missing data and inconsistencies. Accrual rates and extent and accuracy of evaluations and follow-up will be monitored periodically throughout the study period and potential problems will be brought to the attention of the study team for discussion and action.

Random-sample data quality and protocol compliance audits will be conducted by the study team, at a minimum of two times per year, more frequently if indicated.

16.3 Data and Safety Monitoring

The Data and Safety Monitoring (DSM) Plans at Memorial Sloan-Kettering Cancer Center were approved by the National Cancer Institute in September 2001. The plans address the new policies set forth by the NCI in the document entitled “Policy of the National Cancer Institute for Data and Safety Monitoring of Clinical Trials” which can be found at:

<http://cancertrials.nci.nih.gov/researchers/dsm/index.html>. The DSM Plans at MSKCC were established and are monitored by the Office of Clinical Research. The MSKCC Data and Safety Monitoring Plans can be found on the MSKCC Intranet at:

<http://mskweb2.mskcc.org/irb/index.htm>

There are several different mechanisms by which clinical trials are monitored for data, safety and quality. There are institutional processes in place for quality assurance (e.g., protocol monitoring, compliance and data verification audits, therapeutic response, and staff education on clinical research QA) and departmental procedures for quality control, plus there are two institutional committees that are responsible for monitoring the activities of our clinical trials programs. The committees: *Data and Safety Monitoring Committee (DSMC)* for Phase I and II clinical trials, and the *Data and Safety Monitoring Board (DSMB)* for Phase III clinical trials, report to the Center’s Research Council and Institutional Review Board.

During the protocol development and review process, each protocol will be assessed for its level of risk and degree of monitoring required. Every type of protocol (e.g. NIH sponsored, in-house sponsored, industrial sponsored, NCI cooperative group, etc.) will be addressed and the monitoring procedures will be established at the time of protocol activation.

17.1 PROTECTION OF HUMAN SUBJECTS

The study will maintain the privacy of the participant as noted in Section 7.1. The patient will be informed that the study is voluntary and the participant may withdraw at any time. Alternative options for the patient are not to participate in this study and receive no therapy or to receive other treatments that may include hormone therapy, chemotherapy, radiation therapy, targeted therapy, surgery or other investigational therapy. The patient will be informed that there is no known clinical benefit to the immunization under evaluation in this study. Potential benefits include generation of an anti-tumor response by stimulation of the immune system.

The patient is responsible for all costs excluding the sLe^a-KLH plus QS-21 immunization, the evaluation of immune response and the assessment of circulating tumor cells. Potential toxicities are outlined in Sections 11 and 13.

17.2 Privacy

It is the responsibility of the Research Staff to ensure that protocol subjects received the Center's Notice of Privacy Practices. If the subject has not received one, MSK personnel must provide a Notice of Privacy Practices and obtain acknowledgment before the subject participates in the study.

MSKCC's Privacy Office may allow the use and disclosure of protected health information pursuant to a completed and signed Research Authorization form. The use and disclosure of protected health information will be limited to the individuals described in the Research Authorization form. A Research Authorization form must be completed by the Principal Investigator and approved by the IRB and Privacy Board.

17.3 Serious Adverse Event (SAE) Reporting

Any SAE must be reported to the IRB as soon as possible but no later than 5 calendar days. The IRB requires a Clinical Research Database (CRDB) AE report to be delivered to the Institutional SAE Manager ([name]) containing the following information:

Fields populated from the CRDB:

- Subject's name
- Medical record number
- Disease/histology (if applicable)
- Protocol number

Data needing to be entered:

- The date the adverse event occurred
- The adverse event
- Relationship of the adverse event to the treatment (drug, device, or intervention)
- If the AE was expected
- The severity of the AE
- The intervention
- Detailed text that includes the following information:
 - A explanation of how the AE was handled
 - A description of the subject's condition
 - Indication if the subject remains on the study

- If an amendment will need to be made to the protocol and/or consent form

The PI's signature and the date it was signed are required on the completed report.

For IND/IDE protocols:

The CRDB AE report should be completed as above and the FDA assigned IND/IDE number written at the top of the report. The report will be forwarded to the FDA by the Institutional SAE Manager through the IND Office.

